## **6 Study Methods/Procedures**

### **6.1 Study Procedures**

#### **Clinical ED Practice Intervention.**

As part of routine ED care, clinicians conduct delirium screening at bedside to evaluate presence of cognitive impairment in ED who are 65 years and older. The intervention will augment this process to include questions assessing for documented history of dementia or asking the patient, or caregivers present, in the ED if the patient has had any memory or thinking problems in the past year. If clinicians suspect the patient may have cognitive impairment, regardless of the response from patient or caregiver, and the patient has no documented history of dementia, the physicians may refer these patients to available outpatient cognitive evaluation. Referral will occur using EMR outpatient consult requests or by emailing outpatient clinics for available appointments as part of routine patient care referral processes.

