### Outcome Variables

Primary outcome: ED screening and detection rates of delirium, vs. suspect dementia, vs. no cognitive deficits.

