##### **4.2.1 Primary Outcome Variables/Endpoints**

The variables used to assess the primary objective include rates of routine ED screening and detection of delirium, suspected UCID, or no cognitive deficits noted in all older (age 65+ years) ED patients, and rates of successful outpatient referral of patients found to be at risk for UCID.

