#### **6.1.1 Data Collection**

As this is a pilot study, we will gather a convenience sample of 100 participants who are eligible to be referred for outpatient cognitive assessment (50 from each site) will be evaluated. Data will be collected by telephone interview follow-up and chart review for observational characterize subjects, sites, processes, utilization, and outcome endpoints.

Research staff at both sites will contact by telephone the selected participants to conduct two focused interviews at 1-6 weeks and 3 months post-ED visit. The survey will assess the participants experiences through the process, findings of the assessment and the participants follow-up care plan. A retrospective chart review will be conducted on these participants. Trained research staff at each site will conduct chart review in the Electronic Medical Record to determine rates of:

- Healthcare utilization by the patients during the subsequent 30 days in addition to the requested outpatient cognitive assessment, inpatient hospitalizations, and/or ED revisits up to 6 months prior to the current ED visit

- Referral and completion of outpatient cognitive assessment
- New outpatient diagnoses of Alzheimer's Diseases or Related Dementia diagnoses or mild cognitive impairment
- Documentation of Outpatient Cognitive Assessment communication with the patients' primary care providers or other consults of results and recommendations for brain health treatment and management.

Trained research assistants will review the medical records of potentially eligible participants seen in the ED during the study period to assess clinician compliance and acceptance of screening intervention.

Data for this study will be collected, recorded and stored using Redcap (Research Electronic Data Capture). Redcap is a secure, web application designed to support data capture for research studies. Data from any paper study forms will be entered into Redcap and then stored in locked file cabinets restricted to the study team. Data coordination, data management, and database design will occur within the Yale School of Medicine's Program on Aging. See Table 1 for data points that will be collected.

Retrospective chart review will be conducted on a subset of 100 patients as part of study enrollment: We will collect data on a subset of patients meeting inclusion criteria (50 from each site, for a total of 100 subjects).

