Assessment	Screening: Visit (Day 0)	Enrollment: Telephone follow-up #1 (Day 1-45)	Telephone follow-up #2 (Month 3)	Chart Review
ESI level	X			X
ED chief complaint				X
Demographics	X			X
Comorbidities	X			
Disposition from ED (discharged or admitted)	X			X
Discharge to community	X			X
Delirium Screen	X			X
Memory or thinking problem in prior year	X			X
ED referral for outpatient cognitive evaluation requested	X			X
Outpatient appointment scheduled		X	X	X
Outpatient appointment completed		X	X	X
Outpatient cognitive assessment batteries		X	X	X
New Outpatient Cognitive Impairment Diagnoses		X	X	X
Primary Care Brain Health Communication Coordination		X	X	X
Healthcare Utilization		X	X	X
Adverse Events		X	X	X

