## **8.4 Access to Source**

For identification of eligible participants for recruitment and enrollment, research staff will maintain a password protected screening log to track patients who are referred from the ED

for outpatient cognitive assessment. Participants enrolled will be assigned generated participant identification codes to facilitate the de-identification process.

Data will be collected and merged from clinical and administrative reports and chart review by trained research staff into a single Redcap database.

As this use of administrative and retrospective clinical data and chart review are only minimal risk a waiver of signed consent will be requested.

Source data are all information, original records of clinical findings, observations, or other necessary activities in a research study. Source data are contained in source documents. Research staff at the local site will access the following source documents to extract data for medical record abstraction including: ED records, inpatient records, readmission records, consultations, outpatient records (clinical and office charts), medication administration records and other reports.

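### The primary referral rate has no identifiable denominator: no listed data item shows which patients were at risk, so the rate can read too low or too high

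*Combined protocol and SAP*

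**What the plan says.** Section 4.2.1 counts "rates of successful outpatient referral of patients found to be at risk for UCID" among the primary variables, beside detection of suspected UCID. Section 7.2 also plans to measure the proportion at risk in the ED. The readable text gives no operational definition of at risk.

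Section 6.1 (Clinical ED Practice Intervention) adds a memory question to routine delirium screening, but its trigger for referral is "If clinicians suspect the patient may have cognitive impairment, regardless of the response from patient or caregiver", provided no dementia is documented. In that case "the physicians may refer these patients to available outpatient cognitive evaluation".

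On data, section 6.1.1 states: "See Table 1 for data points that will be collected". The table that follows has 16 rows, 8 of them marked at Day 0. These include the delirium screen, "Memory or thinking problem in prior year" and the ED referral request. No row records clinician suspicion or at-risk status. In section 8.4, "research staff will maintain a password protected screening log to track patients who are referred from the ED".

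Section 5.2 says that all older patients in both EDs will be screened, but uses a convenience sample of 100 to evaluate detection and referral rates. Section 5.1 describes the study population as patients who received a referral, whereas section 6.1.1 describes the 100 as eligible for one.

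**The concern.** A referral rate needs both the patients who were referred and those who qualified but were not. Here the second group consists of patients whom a clinician suspected and did not refer. Optional referral means that such patients can exist. The trigger applies whatever the memory answer, so that answer cannot stand in for suspicion: some memory-no patients are suspected, and some memory-yes patients need not be. Without a suspicion item, the analyst must choose a substitute denominator, and the plan does not say which.

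The suspected category in the detection rate has the same weakness if it means clinician suspicion. Both rates matter because sections 4.2 and 7.1 say that the pilot's results will inform effect sizes, sample size and power for the future trial.

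**Working it through.** The plan states no referral or at-risk rate, so there is no figure to reproduce. The check is an illustration on assumed inputs.

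**Assumed inputs, none from the documents.** Per 1,000 screened, discharged patients without known dementia:
- 30% answer yes to the memory question: 300 yes, 700 no.
- Clinicians suspect impairment in 50% of yes and 10% of no answers: 150 + 70 = 220 suspected.
- 70% of suspected patients are referred: 105 + 49 = 154. Unreferred suspected patients: 45 + 21 = 66.

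**True values.** Referral among suspected = 154/220 = 70.0%. Suspected detection = 220/1,000 = 22.0%.

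**Denominator of memory-yes or referred patients (listed items only).** Let L be suspected, unreferred, memory-no patients, who drop out, and U be unsuspected memory-yes patients, who are counted in.
- Reading = referred / (suspected − L + U)
- L = 21 and U = 300 − 150 = 150
- Reading = 154/(220 − 21 + 150) = 154/349 = 44.1%
- Detection would read 349/1,000 = 34.9%

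Table 1 cannot separate the 45 suspected, unreferred memory-yes patients from the 150 unsuspected ones, so all of them enter this denominator.

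**Denominator of referred patients only (the 8.4 log, or a sample made up entirely of referred patients).** Reading = 154/154 = 100%, whatever the true rate. Detection would read 154/1,000 = 15.4%.

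**Direction.** The memory-yes-or-referred reading is too high when L exceeds U, too low when U exceeds L, and correct when they are equal. Take 100 suspected patients and a true rate of 50%, with share q answering no on memory (equal in referred and unreferred), so that L = 100 × q × 0.5:

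| q | L | U = 0 | U = 15 | U = 25 | U = 50 |
|---|---|---|---|---|---|
| 0.1 | 5 | 52.6% | 45.5% | 41.7% | 34.5% |
| 0.3 | 15 | 58.8% | 50.0% | 45.5% | 37.0% |
| 0.5 | 25 | 66.7% | 55.6% | 50.0% | 40.0% |

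Over this assumed range, a true 50% reads anywhere from 34.5% to 66.7%.

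**The case against.** The strongest reply is that at risk may be a screening result and not clinician suspicion. The synopsis states its primary outcome as "ED screening and detection rates of delirium, vs. suspect dementia, vs. no cognitive deficits", and Table 1 collects both the delirium screen and the memory answer. Figure 1, the intervention schematic, is not shown and may hold the definition. This stands as a limit. If at risk means a positive screen, the denominator can be identified, but 4.2.1 should say so, because 6.1 ties referral to suspicion regardless of the memory answer.

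Second, section 6.1.1 plans a wider review of ED records "to assess clinician compliance and acceptance of screening intervention", and section 5.5 seeks access to the records of all older ED patients. Table 1 may be only a participant schedule. That review could recover some suspected, unreferred patients. However, suspicion is not named as an item to abstract, and suspicion that led to no action may not be charted.

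Third, the synopsis lists referral as secondary, with screened patients as denominator, and that rate needs no suspicion item. This is correct and is part of the remedy, but it does not settle the 4.2.1 variable.

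A reader might infer that the referral rate must be overstated, since the patients lost are all non-events. The documents do not support that. It would hold only if unsuspected memory-yes patients could be kept out of the denominator, which needs the missing item. A reader might also infer that the 100 enrolled are certain to give 100%. That follows only if all are referred: the criteria in 5.3 do not require referral, and 6.1.1 says only that the participants are eligible for it.

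**Conclusion.** The concern holds as a problem of identification, not as a bias of known sign. From the listed data, the non-events of a primary rate cannot be found, and the same patients can give very different answers: 44% or 100% against a true 70% in the illustration. The sizes rest wholly on assumed inputs and on at risk including clinician suspicion. An explicit definition in Figure 1 or full recovery through the record review would shrink the gap, possibly to nothing.

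This is more than a missing detail, because section 5.2 takes detection and referral rates from a sample that section 5.1 describes as already referred. The change should be made. Confidence is medium, given the missing figure and the unspecified content of the record review.

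**What to change.** 1. In 4.2.1, define the referral-rate denominator as patients with clinician-suspected UCID and no documented dementia. Add suspicion (yes/no) as an item abstracted in the record review already planned in 6.1.1, covering all unreferred patients or a stated random sample. Report that charting of suspicion may be incomplete. Abstraction is preferable to a live ED field, which could itself prompt referrals.
2. In 5.2 and 7.2, do not estimate detection or referral rates from the 100 enrolled. Report n, % and 95% CI referred among all screened, discharged patients without known dementia, overall and by memory answer and delirium screen. In the illustration this would be 154/1,000 = 15.4% overall, 105/300 = 35.0% for memory-yes and 49/700 = 7.0% for memory-no.

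The cost is one definition, one abstraction item, one descriptive table and some staff time. Suspicion that was never written down will still be missed. Sampling limits the work. In the illustration there are 1,000 − 154 = 846 unreferred charts. If 200 are reviewed and 16 show suspicion (8.0%, Wilson 95% CI 5.0 to 12.6%), the rate is 154/(154 + 846 × 0.080) = 69.5%, with limits of about 59 to 79%. This treats the 154 as fixed and ignores the finite-population correction.

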#### **Standard Care for Outpatient Cognitive Assessment Referral**

The outpatient clinics receiving the ED referrals will reach out to patients to establish and schedule an outpatient evaluation after discharge from the ED.

As part of routine care, the outpatient assessments may include brief neuropsychological tests of cognition memory, language, executive function and attention that may include the Montreal Cognitive Assessment (MoCA), a cognitive screening test to aid in detecting cognitive impairment and evaluations to assess competency in completing instrumental activities of daily living such management of money, behavioral deficiencies and others for standardized consensus evaluation for diagnosis of dementia, cognitive impairment or normal with subtype of impairment. The outpatient evaluations will allow for clinical diagnosis and validation of ED assessment for the presence of dementia or mild cognitive impairment.

In addition, following the evaluation, the outpatient centers will document cognitive impairment diagnoses (if present) and notify patients, caregivers and their primary care providers of results. The centers will utilize available resources to connect patients to their primary care provider with feedback and recommendations for brain health care and management.

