**Secondary outcomes:**

- Rate of screened patients who are referred to outpatient cognitive evaluation
- Rate of screened patients who have outpatient cognitive evaluation
- Rate of screened patients with outpatient evaluation that test positive for dementia

For patients identified as at risk for dementia:

- Referral for additional services
- Rate of primary care follow-up referral
- Rate of cognitive brain health plan, including changes in medications
- New diagnosis of Alzheimer's Disease and Related Dementias

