### **5 Study Participants**

#### **5.1 Study Population**

The study will include all ED patients 65+ years in age seen in the YNHH and Northwestern Memorial Hospital EDs that receive an outpatient clinic referral for a cognitive assessment evaluation over January 2021 – December 2021.

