#### **5.2 Number of Participants**

All patients 65+ years in age seen in both EDs during the study period will be screened in the ED using clinical screening for UCID.

A convenience sample of 100 hundred subjects (50 from each site) will be included for retrospective and prospective observational data via chart review and interview to evaluate rate of UCID detection in the ED, rates of referral for outpatient evaluation, rates of confirmed cognitive impairment or dementia by the outpatient evaluation, and differences across the two sites with processes, utilization, and outcome endpoints.

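### Section 6.1 says outpatient evaluation will validate the ED assessment, but the design can only confirm or refute suspicion in referred patients who attend

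*Combined protocol and SAP*

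**What the plan says.** The statement is in the methods. Section 6.1, under the heading on standard care for outpatient referral, says the outpatient evaluations will permit clinical diagnosis and "validation of ED assessment for the presence of dementia or mild cognitive impairment".

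The route to that evaluation is set out in several places:

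- **Screening covers everyone.** Section 5.2: "All patients 65+ years in age seen in both EDs during the study period will be screened in the ED using clinical screening for UCID".
- **Referral rests on suspicion and is discretionary.** Section 6.1, on the ED practice intervention, starts from clinician suspicion: "If clinicians suspect the patient may have cognitive impairment, regardless of the response from patient or caregiver". If the patient also has no documented dementia, "the physicians may refer these patients to available outpatient cognitive evaluation".
- **Evaluation depends on scheduling.** Section 6.1: "The outpatient clinics receiving the ED referrals will reach out to patients to establish and schedule an outpatient evaluation after discharge from the ED". Completion is itself a secondary outcome.

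The related outcome in the Synopsis is "Rate of screened patients with outpatient evaluation that test positive for dementia". Section 7.2 plans to count the evaluated patients who are diagnosed with cognitive impairment.

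Patients who are not referred contribute only EMR data for comparison (Sections 5.5 and 7) and records reviewed for clinician compliance (Section 6.1.1). Section 7 compares all discharged patients aged 65 or over with those referred. No accuracy or agreement analysis is planned, and neither is any comparison of attenders with non-attenders.

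**The concern.** Validating a screen in the population where it is used requires a reference diagnosis in patients the screen flags and in at least some of those it does not. Here the reference evaluation is reached only after clinician suspicion, a decision to refer, and attendance. Patients lost at any of these steps have no protocol-specified diagnosis.

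The pilot exists to supply estimates for a larger trial (Sections 4.2, 7.1 and 7.2). If many attenders prove to be impaired, the wording in Section 6.1 makes it easy to present that rate as evidence that the ED assessment works. Yet missed cases were never looked for, and non-attenders may differ from attenders. The future trial could then be planned on a yield that describes a selected group.

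**Working it through.** The documents state no accuracy figure, attendance rate, diagnosis rate or precision target, so there is no figure to reproduce. The check asks which cells of the table of ED assessment against outpatient diagnosis are observed, and then illustrates the consequence with assumed rates.

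**Step 1. Observed cells.**

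| Group | Outpatient diagnosis planned? | Contribution |
|---|---|---|
| Suspected, referred, attended | Yes | true and false positives |
| Suspected, referred, did not attend | No | unknown split |
| Not referred (suspected or not) | No | false and true negatives, unobserved |

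With referral as the positive result, every verified patient is positive. Sensitivity computed from verified patients alone is then 100% and specificity 0% by construction, so neither figure carries information.

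**Step 2. Sensitivity and negative predictive value are not identified.** Assume 100 referred, all attending, with 60 confirmed and 40 not, and 1,000 patients not referred. Let q be the share of the non-referred with undetected impairment. Then sensitivity = 60 / (60 + 1,000q) and negative predictive value = 1 − q.

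| q | Sensitivity | Negative predictive value |
|---|---|---|
| 0% | 60/60 = 100% | 100% |
| 5% | 60/110 = 54.5% | 95% |
| 10% | 60/160 = 37.5% | 90% |
| 20% | 60/260 = 23.1% | 80% |

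The study data are identical in all four rows. With 500 non-referred patients the sensitivities are 100, 70.6, 54.5 and 37.5%; with 5,000 they are 100, 19.4, 10.7 and 5.7%. Specificity is also unobserved, but it moves little here (95.2–96.2% with 1,000 non-referred).

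**Step 3. What non-attendance does to the confirmed proportion.** Assume 100 referred, n attending, and x = 0.6n diagnosed. The interval is exact (Clopper–Pearson) for x/n. The bounds over all referred run from x/100 (non-attenders all negative) to (x + 100 − n)/100 (all positive).

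| n | x | Exact 95% CI for x/n | Bounds over all 100 referred |
|---|---|---|---|
| 100 | 60 | 49.7–69.7% | 60% |
| 75 | 45 | 48.0–71.1% | 45/100 to 70/100 = 45–70% |
| 50 | 30 | 45.2–73.6% | 30/100 to 80/100 = 30–80% |
| 30 | 18 | 40.6–77.3% | 18/100 to 88/100 = 18–88% |

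The width of the bounds equals the share not attending (25, 50 and 70 points), whatever proportion is diagnosed. For example, at 50 attending the bounds are 20–70% if 20 are diagnosed and 40–90% if 40 are.

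**Step 4. The denominator.** Section 5.1 limits the population to patients "that receive an outpatient clinic referral for a cognitive assessment evaluation". Section 5.3 does not list referral as a criterion, and Section 6.1.1 describes the 100 as eligible to be referred. If some of the 100 were never referred, the 100 in step 3 is too large. Those patients would still have no planned evaluation, and the absence of a chart diagnosis is not a verified negative.

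**The case against.** The strongest reply is that the study does not set out to measure accuracy. Accuracy is not among the objectives, the endpoints or the planned analyses, and Section 4.2 says no hypotheses are tested. The sentence in Section 6.1 pairs validation with clinical diagnosis, and Sections 2.3 and 5.2 use the language of affirming or confirming suspected impairment. On that reading the clinic simply confirms or refutes the suspicion in the patients it sees, which the design does. The Synopsis rate is already conditioned on having an evaluation, and referral and attendance are counted separately, so a careful reader could derive the bounds.

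Most of this stands, and it limits the point to wording and reporting. It does not remove it. The sentence names the ED assessment, not the individual patient's diagnosis, as the thing validated, and nothing planned shows how attenders differ from non-attenders.

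Three stronger readings are tempting, and the documents do not support them:

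- A reader might infer that the plan will report its secondary diagnosis rate as validation. Section 6.1 does not cite that rate, and the rate does not mention validation. The targets also differ: dementia or MCI in Section 6.1, dementia alone in the Synopsis item.
- A reader might infer that a positive predictive value is the only estimable quantity. Because referral can go against the memory answer, and the data-collection table records the delirium screen, memory item and diagnosis, these can be cross-tabulated among attenders. The result is conditional on referral and attendance and is not accuracy in the ED population.
- A reader might infer that the feasibility outcomes are compromised. Screening, referral and attendance rates do not depend on verifying the screen.

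**Conclusion.** The point holds in a limited form. As designed, outpatient evaluation can confirm or refute ED suspicion in referred patients who attend; it cannot establish the sensitivity or negative predictive value of the ED screen. This follows from who is sent for evaluation and needs no assumed number.

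The sizes shown do rest on assumptions: 100 referred, 60% of attenders diagnosed, the attendance rates, and the number and undetected prevalence of the non-referred. They also take the clinic diagnosis as the reference, although Section 6.1 lets the test battery vary. The bounds address non-attendance only, not the selection of a convenience sample. The consequence is a risk of over-reading when the future trial is planned.

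**What to change.** 1. **Section 6.1.** Replace the claim of validating the ED assessment with *confirmation of suspected impairment among referred patients who complete outpatient evaluation*.
2. **Section 7.2.** Report that proportion separately for dementia and for dementia or MCI, each with an exact 95% confidence interval. Beside it give the bounds over all referred patients, counting non-attenders first as all negative and then as all positive. Label any cross-tabulation of the delirium screen or memory item with diagnosis as conditional on referral and attendance.
3. **Section 7.** Add a descriptive comparison of attenders with non-attenders on items already in the data-collection table: demographics, comorbidities, ESI level, delirium screen and memory item.
4. **Sections 5.1, 5.3 and 6.1.1.** Reconcile referred with eligible to be referred, so that the denominator is fixed before analysis.

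The cost is a narrower claim and one small extra table, with no added patients, visits or data items. If the sponsor does want to validate the screen, a reference evaluation in a random sample of screen-negative patients would be needed, which is a larger change than this point asks for.
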